a. Please describe your data sharing plan, including whether you plan to share your data with your sponsors or with other investigators. Explain whether the shared or disclosed data will be individually identifiable. **Your data sharing plan should be consistent with Sponsor requirements, and the consent document should include a description of your data sharing plan.**

Data from Aim 3 surveys will only be shared and available to study research personnel while it is collected and analyzed. After data has been analyzed and de-identified, it will be available and reported and shared with the CAB as described above in the data analysis plan.

Dissemination activities throughout the K01 research will include conference presentations and peer-reviewed publications. The Johns Hopkins Center for Indigenous Health has a standard proposal, development and approval process, including approval by the White Mountain Apache Tribe (WMAT) review boards. This process will be overseen by [name] with support from the WMAT community collaborator, [name]. Dissemination of study results will also be presented to the relevant advisory boards comprised of WMAT community stakeholders convened at the beginning of the study. The purpose of sharing study results with these groups is to maintain tribal stakeholders as equal research partners in line with community-engaged research, allowing them to provide feedback about interpreting study results, and to collaboratively plan future research projects.

b. Are there laws limiting data sharing in the country where the research site(s) is located? If yes, please address those limitations and how you will comply with them.
 No.

c. Will you make your data publicly available? If yes, what is your plan for de-identification?
 No.

d. Will you deposit it into a repository for broader use? If yes, identify the repository and provide information about the data protections.
No.

H. JHM Clinical Records:

Will you use clinical data of 500 records or more from Johns Hopkins Hospital and its affiliates?
 Yes * No

**If yes, please complete the JHM Data Security Checklist available on the JHSPH IRB website: www.jhsph.edu/irb and upload a copy of the checklist to the "Miscellaneous" section.*

VII. Risks of the Study:

A. Describe the risks, discomforts, and inconveniences associated with the study and its procedures, including physical, psychological, emotional, social, legal, or economic risks, and the risk of a breach of confidentiality. **These risks should be described in the consent documents.**

Aim 3: For the surveys in Aim 3, the primary risk to participants is the time it takes to complete the surveys. There is a small potential for participants to feel distressed by the questions, for example, if they have recently lost a relative some of the questions asking about connections to relatives may create some discomfort. Because all of the questions are strengths-based and focus on positive outcomes, we anticipate that the potential risk of emotional or psychological discomfort will be very low.

B. Describe steps you will take to mitigate or minimize each of the risks described above. Include a description of your efforts to arrange for care or referral for participants who may need it.

Aim 3: Participants will be informed that they may skip any questions in the survey that they do not wish to answer and that they can stop at any time if the questions make them uncomfortable. If any participant does become distressed during the completion of a survey, a break will be provided or the procedure will be stopped, and the research staff will work with the participant to reduce the participant's distress. If these approaches do not reduce the participant's distress, the research study staff person will ask if the participant wishes to address the distress in another manner and will facilitate the participant's request when possible. Local research staff who are CMHSs working as part of the local Celebrating Life team regularly encounter individuals in distress and are trained and have extensive experience supporting these individuals and can be called in to help support participants if needed, including providing referrals to local services if necessary.

In addition, field staff can enlist the Principal Investigator (PI), [name] [name], a Licensed Clinical Psychologist, to talk with the participant in person (if [name] is on site) or via phone and facilitate appropriate referrals for the participant if necessary. All research staff have the PI's cell phone number to contact her for these types of events 24 hours a day. All research staff also have [name] mentors' and colleagues at Johns Hopkins Center for Indigenous Health ([name]; [name]) cell phone numbers to serve as back-up should they be unable to reach the PI.

C. Describe the anticipated frequency and severity of the harms associated with the risks identified above; for example, if you are performing "x" test/assessment, or dispensing "y" drug, how often do you expect an "anticipated" adverse reaction to occur in a study participant, and how severe do you expect that reaction to be?

Aim 3: We anticipate minimal frequency and low severity of the harms associated with the risks above based on previous Apache-JHU studies with this population.

D. Describe the research burden for participants, including time, inconvenience, out of pocket costs, etc.

Aim 3:

The main burden for participants in the survey will be time.

E. Describe how participant privacy, and if relevant – family privacy - will be protected during data collection if sensitive questions are included in interviews, or if study visits occur in the home setting.

Aim 3: The survey does not include sensitive questions and study visits will not occur in the home.

F. Levels of COVID-19 community transmission will vary considerably by geography and over time, and therefore, the responses to the pandemic may also vary. The risk of COVID-19 to study staff and participants from in-person research activities can be mitigated by appropriate study procedures. If you are conducting in-person research activities, please indicate the protections you plan to implement at your research site(s):

- Not applicable
- COVID testing of staff
- COVID testing of study participants
- Indoor masking/wearing PPE
- Social distancing for indoor activities
- Symptom screening of staff
- Symptom screening of study participants
- Vaccination of research team members
- Other procedures/comments: Masks and hand sanitizer are offered to all participants during in-person study activities.

VIII. Direct Personal and Social Benefits:

A. Describe any potential direct benefits the study offers to participants (“payment” for participation is not a direct personal benefit).

Aim 3: Participants may benefit by understanding and feeling like they are contributing to supporting youth in their community by engaging in this research. They may enjoy some of the survey questions which ask about many positive topics (e.g., self-esteem, feeling connected).

B. Describe potential societal benefits likely to derive from the research, including value of knowledge learned.

American Indian/Alaska Native youth are the age and racial/ethnic group at highest risk for suicide nationally. The Elders' Resilience Curriculum, the focus of this study, is an innovative, culturally grounded suicide prevention intervention that targets modifiable cultural protective factors. Identifying and understanding its core components, producing an empirically-driven Indigenous youth resilience theoretical model and matched culturally informed assessment battery, and conducting a pilot evaluation (Aim 3) will lead to a critically needed fully-powered R01 effectiveness study. Collectively, this research is necessary for scaling this promising community-driven prevention intervention to other American Indian/Alaska Native communities to reduce youth suicide.

Capacity building: This study focuses on a community-driven suicide prevention intervention that is delivered by local Elders to youth in schools. Given numerous challenges in mental health care access and delivery of culturally-informed care, this approach has enormous benefit for participants on tribal lands. In addition, tribal capacity building is evidenced by White Mountain Apache community mental health specialists, including [name], who will serve as research study staff.

Scientific field: This study will provide answers to questions about identifying core components of culturally grounded mental health prevention interventions, how core components impact mechanisms of change within these interventions, and important contributions to expand the measurement development/adaptation field to evaluate American Indian/Alaska Native youth interventions. There is a dearth of research in this area, as well as generally about protective factors against suicide for American Indian/Alaska Native youth.

Policy: Knowledge gained from this study can be used to inform evidenced-based and culturally congruent local policies and programs. Community stakeholders will be involved with the initial and ongoing review of study protocols. Their collective involvement will be critical, thus allowing for real-time policy influence.

The proposed study will make significant contributions to the field of Prevention Science by understanding how an innovative, culturally grounded suicide prevention intervention, promotes mental health and reduces suicide for American Indian youth. This research includes an understudied population in a low resource setting targeting an age and racial/ethnic group at highest risk for suicide in the U.S. Thus, this study will yield valuable knowledge about how community-driven, culturally-based, upstream solutions to suicide outside conventional mental health care settings can be valuable in this context and how it can be generalized to other similar contexts.

IX. Payment or Token of Appreciation:

A. Do you plan to provide a non-monetary token of appreciation (food, soap, tea, chlorine tablets, etc.) to study participants? If yes, please describe below.

Aim 3: Participants will not receive any non-monetary tokens of appreciation.

B. If you plan to provide a monetary payment, describe the form, amount, and schedule of payment to participants. Reimbursement for travel or other expenses is not “payment,” and if the study will reimburse, explain.

Aim 3: Students who complete the survey in Aim 3 will receive a \$25 gift card for each survey they complete (up to three \$25 gift cards if they complete all three surveys – baseline, midline, and endline). Students who complete all three surveys may receive up to \$75 in gift cards.

C. Include the possible total remuneration and any consequences for not completing all phases of the research.

There are no consequences for not completing all phases of the research, participants may choose to end their participation at any time without penalty and will receive payment for any completed study activities.

For **Aim 3**, total remuneration for each participant is up to \$75 (\$25 gift card per survey, three surveys).

X. Study Management:

A. Oversight Plan:

1. Describe how the study will be managed.

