A. Provide a BRIEF overview of your study design and methods. The study design must relate to your stated aims/objectives. DETAILS WILL BE REQUESTED LATER. *If your study also involves analysis of existing data, please complete Section XI, "Secondary Data Analysis of Existing Data" in the last part of this research plan. If your study ONLY involves analysis of existing data, please use the research plan template for secondary data analysis (JHSPH IRB Research Plan for Secondary Data Analysis of Existing Data/Specimens)*

Aim 3

Aim 3 of the project includes a pre-/post-test design evaluation of the Elders' Resilience

Curriculum using culturally adapted measures. The ERC is a monthly curriculum delivered by Elders to youth in classrooms. Delivery of ERC curriculum content will be monitored by WMAT CMHSs using session summary sheets. The PI and a research assistant will check session summary sheets to check if core components were delivered with fidelity and to compare against core components determined in Aim 1.

A survey comprised of these culturally adapted measures will be administered to youth in schools where the ERC is delivered at three timepoints – once at the beginning of the school year, once during the middle of the school year, and finally at the end of the school year. Change in outcomes over time as students receive the ERC lessons will be assessed.

B. Provide a sample size and a justification as to how you arrived at that number. If you use screening procedures to arrive at a final sample a table may be helpful.

Aim 3

For the pre-/post-test survey in Aim 3 we will aim to recruit and enroll up to $N=200$ youth ages 9-14 from 5-10 classrooms where the ERC is delivered. This sample size is based on feasibility and convenience (e.g., based on the classroom sizes in schools where the ERC is delivered) and leaves flexibility in case classroom sizes are larger than anticipated.

IV. Participants:

Describe the study participants and the population from which they will be drawn. Specify the inclusion and exclusion criteria. If you plan to include children, note their ages and whether you will include children in foster care. Note if the participants are particularly vulnerable in terms of cognitive limitations, education, legal migration status, incarceration, poverty, or some combination of factors.

A. Inclusion Criteria:

Aim 3:

Inclusion criteria for participants in the pre/post study:

- 1) Be between 9-14 years of age

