Rosenberg self-esteem scale	The Rosenberg self-esteem scale [21] is comprised of 10 self-report items that measure global self-worth through asking about positive and negative self-feelings. The scale has been used with adolescent AIs with good reliability (alpha=0.84; [22]).
Self-reported academic outcomes	Four self-report items to assess grades, academic performance, attitude toward school, and educational goals will be used to measure academic outcomes. These items come from a research study with AI adolescents [22].
Self-reported health ratings	Three questions asking participants to self-report their overall physical, mental, and spiritual health assess overall health. These questions were used in previous research with Indigenous young adults [17].
Demographics	Six questions asking about basic demographic information were created in collaboration with WMAT community partners and included here.

2. Describe the number and type of study visits and/or contacts between the study team and the participant, how long they will last, and where/how they will take place.

Aim 3:

Survey: Students who participate in the aim 3 survey will spend approximately 15 minutes interacting with study staff to obtain youth assent. Student participants will be asked to complete the survey at three timepoints, once in the beginning of the school year (baseline), once approximately halfway through the school year (midline), and once at the end of the school year (endline). It is estimated that each of these surveys will take students between 20-60 minutes to complete, meaning study participation in the survey would take a total of 1-3 hours of time across all data collection timepoints. At each timepoint the survey will be administered to students in schools. We will collaborate with the schools to schedule an appropriate time to come in and administer the survey with students in their classrooms. CMHSs supporting this study will help administer the survey in classrooms by providing instructions and distributing paper survey packets. CMHSs will be available to answer any questions a student might have to help them complete the survey and

will observe and monitor the classroom to ensure students are filling out the surveys independently and that all survey data remains anonymous and confidential.

3. Describe the expected duration of the study from the perspective of the individual participant and duration overall.

Aim 3:

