The overall goal of the analysis will be to assess for change in outcomes across time from all three survey timepoints (baseline, midline, and endline) using a pre/post analysis. All responses will be analyzed with SPSS software to examine internal consistency of each scale, item and scale level response distributions, inconsistencies in responses, and missing data patterns. Change over time in key outcomes (see table above listing outcomes) will be assessed. Session summary forms will be reviewed to assess intervention delivery fidelity and consistency across lessons. Cognitive interview responses will be compiled and analyzed to assess item fit and comprehension and to make potential improvements or changes to future surveys.

The original plan was to run an Observed Change Score Model where we created difference scores from baseline to midline and midline to endline and examined which predictors explained changes during those two periods.

After running these models using SEM, the models were unstable and therefore the results were biased and untrustworthy. Thus, I pivoted to conducting a Linear Mixed Model or Mixed Effects Model that could account for the repeated measures structure with only one group and allows participants to vary at baseline. Due to the number of participants in the data set, I wasn't confident that this model would run when first deciding on a model, but it ended up running without issue. I checked the assumptions for running the model with our data and all of the assumptions were met. The assumptions are:

Linearity: Check with residuals vs predictors.

Independence: Accounted for by random effects but plotted residuals over time to check.

Homoscedasticity: Plot residuals vs fitted values.

Normality of Residuals: Histogram and Q-Q plot of residuals.

Normality of Random Effects: Plot random intercept distribution.

The equation for the model is as follows

$$RFL = \beta_0 + \beta_1 Midline + \beta_2 Endline + \beta_3 AWOC + \beta_4 CCS + \beta_5 CCS ID + \beta_6 CES + \beta_7 LWI + \beta_8 IC + \beta_9 MMS + \beta_{10} RES + \beta_{11} SDI + u_i + e_{ij}$$

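### The Reasons for Life model has no age term, so its nine scale slopes can be confounded by age across children aged 9 to 14

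*Combined protocol and SAP*

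**What the plan says.** The SAP (Aim 3) first planned difference scores between adjacent waves and "examined which predictors explained changes during those two periods". It replaced them with a "Linear Mixed Model or Mixed Effects Model that could account for the repeated measures structure with only one group". The outcome is Reasons for Life. After an intercept and the Midline and Endline indicators, the equation continues "\beta_3 AWOC + \beta_4 CCS + \beta_5 CCS ID + \beta_6 CES + \beta_7 LWI" and ends "\beta_8 IC + \beta_9 MMS + \beta_{10} RES + \beta_{11} SDI + u_i + e_{ij". That makes nine scale slopes (beta3 to beta11), one child random intercept and a residual. No centring, child-mean term, age or other demographic term is shown.

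The inclusion criteria (protocol section IV.A) require a child to "Be between 9-14 years of age". Section III.B plans for up to 200 "youth ages 9-14 from 5-10 classrooms where the ERC is delivered". The measures table in section V.C.1 adds that "Six questions asking about basic demographic information were created in collaboration with WMAT community partners", asked at baseline only; the six items are not listed. Neither section V.C.4 nor the SAP says how they enter the analysis. The identifier table in section VI.A has the row that includes birth dates checked under data collection.

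**The concern.** The SAP describes the random intercept as one that "could account for the repeated measures structure with only one group and allows participants to vary at baseline", which can be read as protection against stable differences between children. It is not. The model assumes the intercept to be independent of the predictors, so it absorbs only variation unrelated to the scales. A stable trait linked to both Reasons for Life and a scale still enters that scale's slope through the between-child part. The SAP's five assumption checks are plots of residuals and of random intercepts; none examines whether the child effect is related to the predictors.

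Age is the obvious candidate trait in a sample spanning 9 to 14 years. The change of model created the exposure. If age adds a constant amount to a child's level at every wave, it drops out of a difference score; in a model of levels it stays.

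Aim 3 is meant to try out the theoretical model ahead of a fully powered trial. If the slopes are read as evidence on which constructs go with Reasons for Life, age could lend false support to some of them.

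**Working it through.** The documents state no power, alpha or effect size, so there is no figure of the plan's own to reproduce.

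**Inputs from the documents.** Three waves (T = 3), nine slopes (11 − 3 + 1 = 9), up to 200 children, ages 9–14.

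**Assumptions.** Standardised scores; intraclass correlation (ICC) 0.6; age correlated r with Reasons for Life and r with every scale; all true scale effects zero; two-sided 5% tests.

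**Step 1: size of the spurious slope.** The random-intercept fit weights between-child information by (1 − θ)² = 0.4 / (0.4 + 3 × 0.6) = 0.182. Put c = 3 × 0.182 = 0.545. For one scale:

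slope = c r² / [(T − 1)(1 − ICC) + (1 − θ)²(T × ICC + 1 − ICC)] = 0.545 r² / (0.8 + 0.4) = 0.545 r² / 1.2

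At r = 0.3 this is 0.0491 / 1.2 = 0.041 (simulated: 0.042).

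With nine scales whose pairwise between-child covariance is v, the denominator becomes 1.2 + 8cv. If the scales are related only through age, v = r². If they also share half of their non-age between-child variance, v = r² + 0.5(0.6 − r²). At r = 0.3:

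- No overlap: 0.0491 / (1.2 + 8 × 0.545 × 0.09) = 0.0491 / 1.593 = 0.031.
- Half shared: 0.0491 / (1.2 + 8 × 0.545 × 0.345) = 0.0491 / 2.706 = 0.018.

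**Step 2: false-positive rates.** Simulation of the SAP equation, 200 children, 400 replicates per cell:

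| r | Scale overlap beyond age | Slope, formula | Slope, simulated | Per-slope rate | Any of nine | Per-slope rate with age added |
|---|---|---|---|---|---|---|
| 0 | none | 0 | 0.000 | 5.1% | 39% | 4.8% |
| 0.1 | none | 0.004 | 0.004 | 5.8% | 41% | 5.1% |
| 0.2 | none | 0.016 | 0.015 | 7.0% | 46.5% | 5.0% |
| 0.3 | none | 0.031 | 0.031 | 11.9% | 70% | 5.1% |
| 0.4 | none | 0.046 | 0.049 | 22.5% | 91.5% | 5.6% |
| 0.2 | half shared | 0.008 | 0.008 | 5.4% | 37.5% | 5.2% |
| 0.3 | half shared | 0.018 | 0.018 | 6.7% | 46% | 5.7% |
| 0.4 | half shared | 0.031 | 0.030 | 10.6% | 69.5% | 5.3% |

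The any-of-nine column must be read against 1 − 0.95⁹ = 37%, which is multiplicity, not age. Further runs gave 5.4–11.4% per slope at r = 0.3. The gap between 11.4% and 11.9% is simulation error: √(0.119 × 0.881 / 3,600) = 0.5 points. With 100 children and no overlap, the per-slope rate is 6.7%, 8.7% and 13.0% at r = 0.2, 0.3 and 0.4.

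**Step 3: joint test of nine slopes (not in the SAP), 200 children.** At r = 0.2 it rejects in about 7–12% of runs. At r = 0.3 it rejects in 34–39% with no overlap, 22% with half of the non-age between-child variance shared, and 12% with half shared both between and within children. A share of 0.7 brings it to 9%. With age added it is 4.4–5.9%.

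**Step 4: wave terms.** Age differences between children are constant across waves, so age is unrelated to Midline and Endline when the same children are followed.

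**The case against.** The strongest reply is that the harm is hypothetical and small. Nothing in the documents shows that age is related to Reasons for Life or to any scale. The measures table assigns several scales to the same constructs (identity, cultural continuity, community connectedness), so overlap is likely, and overlap pulls the per-slope rate towards 5%. When at least 0.3 of the non-age variance was shared both between and within children, it stayed at 5.0–5.7%. The SAP states no significance rule, the stated goal is change over time, and this is a one-group pilot. All of that stands and limits the size of the point. It does not rescue the random intercept as a control for age, and it gives no reason to leave age out.

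Four stronger readings are tempting and unsupported:

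- A reader might infer that the slopes already estimated are artefacts of age. The documents give neither those estimates nor any age correlation.
- A reader might take the upper end of the joint-test range as the plan's error rate. The SAP has no such test, and that end requires scales that overlap only through age.
- A reader might infer that gender and other demographics were collected and ignored. The six items are not listed.
- A reader might extend the bias to the estimates of change over time. Step 4 shows why it does not carry over. Dropout that varies by age could alter this, but the documents do not report it.

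**Conclusion.** The point holds as a conditional one. The model as written leaves beta3 to beta11 open to confounding by age, and the move from difference scores to levels removed a safeguard. With 200 children, ICC 0.6 and no true scale effects, the per-slope false-positive rate is about 5–7% at r = 0.2 and 5–11% at r = 0.3. The joint test would reject in about 7–12% and 12–39% of runs for overlap up to half. The effect is negligible at r = 0.1. All correlations, the ICC and the degree of overlap are assumptions, as is the same r for every scale. Treating the nine slopes as the test of the theoretical model is an inference from Aim 3 and from the purpose of the abandoned model; the SAP does not say so.

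**What to change.** Add baseline age, continuous, as a fixed effect in the Reasons for Life model. Add gender only if it proves to be one of the six demographic items. Because the SAP reports that the model has already been run, show the age-adjusted fit beside the original and label it as added afterwards.

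The cost is one parameter (two with gender). No new data should be needed: age has to be known for eligibility, and the identifier row covering birth dates is checked, although that row covers several kinds of date. If age turns out to be unrelated, little is lost: at r = 0 the per-slope rates were 5.1% without age and 4.8% with it.

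Age adjustment removes confounding by age only. As an optional addition, splitting each scale into the child's mean and the deviation from it would protect the within-child slopes from other stable traits. In the simulation those slopes stayed at 4.4–5.6% even without age. This costs nine further parameters.
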